If resection of fibroids and polyps does indeed improve reproductive performance, then this would have a potential influence on existing fertility pathways. For example, the NICE guidelines for fertility management suggest that IVF is the optimum treatment for women with unexplained infertility (25). Funding for IVF however is variable and inconsistent across the UK and is often limited to a single cycle. If women with submucous fibroids or polyps associated with unexplained infertility were to benefit from resection of these lesions, then in many cases IVF treatment could be avoided with consequent cost savings to both the NHS and to self-funding patients.–There is a current trend towards local authorities reducing funding for fertility treatments, thus increasing the burden on patients to fund this treatment themselves. Given this, and the emotional and medical side effects of receiving such treatments, it is imperative that evidence is created to guide clinicians and patients on the effects of hysteroscopic resection so that they can make an informed decision in relation to the patient's chances of live birth (30). There is therefore a current urgent need for a well-designed definitive study examining the effect of hysteroscopic resection of submucous fibroids and polyps in the two distinct populations of women with infertility and women with recurrent miscarriage, whether being managed expectantly or with active fertility interventions.

3. Aims and objectives

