6.1 Patients randomised to Intervention Group

Hysteroscopic resection of submucous fibroids and endometrial polyps is currently undertaken routinely in the NHS for women suffering from miscarriage or infertility.

In order for this study to be applicable to the wider NHS, a pragmatic approach will be taken, and hence we will accommodate local hysteroscopic procedures conducted at the participating centres using existing surgical techniques and setups. Techniques will include the use of bipolar or monopolar resectoscopes, hysteroscopic morcellators or scissors or polyp snares. The procedure may be performed in an outpatient or inpatient setting. For large abnormalities, further surgical procedures may be required. Type 0 and Type I submucous fibroids are more easily resectable than Type II. Clinical / operator judgement will be used to determine the intra-cavitary portion that is resectable for Type II fibroids. As per usual practice, women randomised to receive the intervention will be asked to use contraception prior to hysteroscopy taking place, if applicable. A pregnancy test may also be undertaken. This is in line with routine clinical care and the World Health Organisation (WHO) checklist prior to resection (33). In the event that a patient allocated to intervention has a positive pregnancy test before receiving hysteroscopic resection, the patient will remain in the trial and followed-up as per the schedule in 9.1.

Scheduling treatment

For participants allocated to the intervention group, sites should aim to schedule the appointment for hysteroscopic resection within the 18-week patient pathway. However, with the current COVID-19 pandemic the procedure should be scheduled within the site's own current guidelines. Participants expecting to receive other fertility treatments e.g. IVF, ovulation induction, IUI, Donor Sperm Insemination, ICSI or medications e.g. clomid, should commence with this treatment as soon as possible following hysteroscopic resection. This does not include any research infertility interventions as these are exclusion criteria.

Compliance

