8.3 Secondary outcomes

Clinical outcomes

2. LBR at 24 months post-randomisation;
3. Time from randomisation to live birth (LBR);
4. Time from randomisation to pregnancy;
5. Clinical pregnancy (an observation of viable intrauterine pregnancy with a positive heart pulsation seen on ultrasound at/after 8 weeks gestation); miscarriage (spontaneous pregnancy loss, including pregnancy of unknown location (PUL), prior to 24 weeks gestation); premature labour (labour that happens before the 37th week of pregnancy); multiple birth (multiple live births per mother, e.g. twins or triplets etc.); still birth (delivery of a still born foetus showing no signs of life after 24 weeks gestation); and ectopic pregnancy rates (pregnancy outside the normal uterine cavity);
6. Detail of hysteroscopy received, including: number of hysteroscopic procedures received, duration of time post-surgery abstaining from sexual intercourse, type of resection performed (i.e. use of electrical energy device, morcellation devices and others). This applies to intervention arm only;
7. Patient satisfaction. A questionnaire will be designed with input from our PPI co-applicants and the Jessop Wing - Reproductive Health Research Public Advisory Panel to assess general patient satisfaction with the fertility treatments received since randomisation into the trial. The questionnaire will be sent to intervention arm participants and will concentrate on a) waiting time for treatment, b) satisfaction and tolerability of procedures received, c) thoughts on pre and post procedure information provided, d) psychological support, e) logistical family implications of surgery, f) procedure related anxiety;
8. Details of fertility treatments received, including details of medications received (e.g. clomid) and assisted reproductive techniques received (e.g. type of treatment, fresh or frozen cycle, quality and number of embryos transferred during IVF, IUI or ICSI cycle);

9. Incorrect diagnosis/absence of abnormalities at surgery. Where techniques other than diagnostic hysteroscopy have been used to visualise the endometrial polyp or submucosal fibroid, data will be collected regarding any false diagnoses of endometrial polyps/submucous fibroids;
10. Type of submucous fibroid (type 0, 1, or 2);
11. Number of participants in the control arm who undergo resection.
12. COVID-19 vaccination status (1st, 2nd, booster, approximate date and type of vaccine);

Safety outcomes

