- Time to live birth, time to pregnancy, pregnancy rate, miscarriage, premature labour, multiple birth, still birth, ectopic pregnancy, adverse events, details of fertility treatments received, COVID-19 vaccination status and health resource use.
- Adverse event information

The health resource use questionnaire will be sent directly to the patient from the CTRU via post or online.

24 month post-randomisation (and up to LPLV)

Members of site staff will be asked to record the following from patients' medical notes and / or telephone contact with the participant;

- Adverse event information
- Time to live birth, time to pregnancy, pregnancy rate, miscarriage, premature labour, multiple birth, still birth, ectopic pregnancy, adverse events, details of fertility treatments received and COVID-19 vaccination status.

The health resource use questionnaire will be sent directly to the patients from the CTRU via post or online.

Table 2 – Data collection time points

	Eligibility assessment	Baseline/ randomisation	Directly post-hysteroscopy #	6 months*	15 months*	24 months*	Post 24 months to Last Patient Last Visit (LPLV)	Long term (minimum 5 years post randomisation)
Demographics – age, fertility markers, previous fertility treatment received, type of infertility (infertility/recurrent miscarriage), BMI, smoking status.	MN	IP/MN						
Details of uterine abnormalities (size, grade)	MN	MN	MN					
Patient satisfaction			Q#					
Live birth rate (primary outcome)					T/MN (primary outcome)	T/MN		MN/NHSD
Time to live birth					T/MN	T/MN	MN	
Time to pregnancy				MN	T/MN	T/MN	MN	MN/NHSD
Pregnancy rate				MN	T/MN	T/MN	MN	MN/NHSD
Miscarriage				MN	T/MN	T/MN	MN	MN/NHSD
Premature labour					T/MN	T/MN	MN	

HELP Fertility?

Multiple birth					T/MN	T/MN	MN	
Still birth					T/MN	T/MN	MN	MN/NHSD
Ectopic pregnancy				T/MN	T/MN	T/MN	MN	
Adverse events; obstetric, gynaecological or procedure related complications			IP/T/MN	T and MN	T and MN	T and MN	MN	
Obstetric outcomes				T/MN	T/MN	T/MN	MN	
Details of hysteroscopy received (intervention arm only)			MN	MN	MN	T/MN	MN	MN/NHSD
Details of fertility treatments received (clomid, IVF, IUI etc.)				MN	MN	MN	MN	MN/NHSD
Health resource use,		Q/MN		Q/MN	Q/MN	Q/MN		
Patient cost questionnaire			Q					
Time post surgery abstaining from sexual intercourse [#]				T/Q				
COVID-19 vaccination status (1 st , 2 nd , booster, approximate date and type of vaccine)		T/Q		T/Q	T/Q	T/Q	T/Q	

HELP Fertility?

* Time points measured from randomisation

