The per protocol population for those randomised to receive hysteroscopic removal of submucous fibroids or endometrial polyps is defined as a patient a) attending the clinic for the hysteroscopic excision of submucous fibroids and or endometrial polyps and b) receiving the procedure per protocol (following the sites usual procedures for hysteroscopic removal of submucous fibroids and / or endometrial polyps) within the first six-months post-randomisation. The PP population for those randomised to the control group and not to receive hysteroscopic removal of submucous fibroids or endometrial polyps is defined as a patient a) attending the clinic and b) not undergoing hysteroscopic removal of submucous fibroids or endometrial polyps procedure per protocol within the first six months post-randomisation.

Safety and adverse events

Adverse events including serious adverse events (death; hospitalization (initial or prolonged); disability or permanent damage; other important medical events), will be reported for each randomised group and compared between the two groups using a Fisher's Exact test or Chi-squared test (as appropriate). A 95% confidence interval (CI) for the difference in adverse event rate between the groups will also be calculated.

Sub-group analyses

An exploratory sub-group analysis using multiple logistic regression, with the primary outcome LBR, will look for an interaction between treatment group and the following sub-groups: a) infertility/recurrent miscarriage and b) type of fertility treatment received. A sub-group analysis looking at interaction between treatment group and type of submucous fibroid may be carried out if a sufficient number of control participants undergo diagnostic hysteroscopy, as part of site's usual diagnostic procedures, with fibroid type identified.

Analysis of time to event outcomes

Within the main trial period all women recruited to the trial will be followed up for a minimum of 2 years post-randomisation. Given the study recruitment will take 2.5 years then the first recruited women will have up to 4.5 years follow-up. Women will be censored at the last known date of follow-up if they have not had a live birth/clinical pregnancy.

Intervention waiting times and withdrawal from randomised treatment

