The primary outcome analysis (the LBR at 15 months post-randomisation) may be affected by withdrawal or by women not receiving the randomised treatment allocation. That is if participants randomised to the intervention do not receive the resection by approximately 3-months post-randomisation we may not have a valid, reliable, and robust estimate of the effect of actually receiving the intervention. Rather we will just have an estimate of the policy of randomising participants to receive resection or not. Similarly, if participants randomised to the control treatment withdraw from the control treatment and receive a resection in the first 6-months post-randomisation then again we will not have a valid reliable and robust estimate of the effect of not receiving the intervention. If a substantial proportion of participants withdraw before 6 months post-randomisation or do not receive their treatment allocation by 3-post-randomisation then in these circumstances the comparison of the LBR outcome at 15 month post-randomisation outcome between the randomised groups may not produce a reliable and valid estimate of the effect of resection of fibroids / polyps or not.

The secondary outcome of time to live birth could also be affected by this. Statistical adjustment methods such as rank preserving structural failure time models and inverse probability weighting (IPCW) will be used to adjust for potentially informative withdrawal from randomised treatment (or withdrawal from the trial) in secondary analyses of the end of trial follow up data. These methods have been shown to perform well in a range of scenarios related to informative drop-out such as treatment crossover, though are associated with limiting assumptions (43–45). A subgroup analysis will include women with infertility/recurrent miscarriage. We also expect that IVF could be important and may differ between treatment arms. If this is the case we will undertake an analysis adjusting for IVF to estimate the relative effectiveness of surgery vs no surgery in the absence of IVF, using inverse probability of censoring weights.

Analysis of long term outcomes

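### Subgroup (b), type of fertility treatment received, is measured after randomisation and may differ by arm, so its interaction with treatment can create, exaggerate or hide effect modification

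*Protocol*

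**What the plan says.** Under Sub-group analyses, section 11.2 of the protocol plans a logistic regression on the primary outcome, labelled exploratory. According to the protocol it "will look for an interaction between treatment group and the following sub-groups: a) infertility/recurrent miscarriage and b) type of fertility treatment received". So the choice of variable is already made in the protocol.

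Other sections show what kind of variable (b) is:

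- Section 8.3 lists it as secondary outcome 8: "Details of fertility treatments received, including details of medications received (e.g. clomid) and assisted reproductive techniques received".
- Table 2 in section 9.1 has a row "Details of fertility treatments received (clomid, IVF, IUI etc" with entries at 6, 15 and 24 months and later, and none at baseline. The baseline row covers "previous fertility treatment received, type of infertility (infertility/recurrent miscarriage", which is past treatment and type of infertility. Table 2 lists no item for planned treatment.
- Section 6.1 says that intervention women expecting other fertility treatment "should commence with this treatment as soon as possible following hysteroscopic resection". Section 6.2 tells controls to start or resume it as soon as possible after randomisation.
- Section 2.1 argues that, if women with unexplained infertility benefit from resection, "then in many cases IVF treatment could be avoided with consequent cost savings".
- Later in section 11.2: "We also expect that IVF could be important and may differ between treatment arms". If this happens, an analysis with inverse probability of censoring weights is planned, to estimate the effect of surgery in the absence of IVF.

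**The concern.** A subgroup comparison keeps the protection of randomisation only if membership is fixed before allocation. Here a woman's level of (b) is settled during follow-up, and in two ways it may depend on her arm. Resection may come first and push IVF later. And a woman who conceives before her IVF begins may be counted as not having had IVF, so the outcome itself can decide the subgroup. Women who received IVF in one arm may then be a different kind of woman from those who received it in the other.

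Whether resection helps women going on to IVF, or only those conceiving without it, is a question clinicians would act on even from an exploratory result. An interaction on treatment received could give a misleading answer in either direction. The bias would not shrink with a larger sample.

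**Working it through.** **Inputs from the protocol.** Control live birth rate 10% (section 11.1), 1:1 allocation (section 7), 560 women per trial. The 560 reproduces: with pooled variance, n = [1.960·√(2·0.15·0.85) + 1.282·√(0.10·0.90 + 0.20·0.80)]² / 0.10² = 266 per group, and 532/0.95 = 560. It serves here only as the trial size. The protocol gives no figure for IVF uptake, for the delay, or for the interaction, so those below are assumptions.

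**Step 1. A case with no effect of any kind.** Assume resection does nothing, overall live birth is 10% in both arms, and 50% of controls receive IVF. A share d of women would receive IVF under control but not under intervention, and their live birth rate is m. The rate in all other women is p = (0.10 − d·m)/(1 − d).

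For d = 10% and m = 30%:

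- p = (0.10 − 0.03)/0.90 = 0.0778.
- Control, IVF: (0.40·0.0778 + 0.10·0.30)/0.50 = 0.1222. Control, no IVF: 0.0778.
- Intervention, IVF: 0.0778. Intervention, no IVF: (0.50·0.0778 + 0.10·0.30)/0.60 = 0.1148.
- Odds ratio with IVF: (0.0778/0.9222)/(0.1222/0.8778) = 0.61. Without IVF: (0.1148/0.8852)/(0.0778/0.9222) = 1.54. Ratio of odds ratios: 0.39.
- Cell sizes at 280 per arm are 140, 140, 112 and 168. The standard error of the log ratio is √Σ 1/[n·p(1 − p)] = 0.59, so z = ln(0.39)/0.59 ≈ −1.6. A two-sided 5% test rejects in 35% of trials.

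Over a range of d and m, ratio of odds ratios and rejection rate:

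| d | m = 10% | m = 20% | m = 30% |
|---|---|---|---|
| 5% | 1.00; 5% | 0.80; 7% | 0.64; 12% |
| 10% | 1.00; 5% | 0.63; 13% | 0.39; 35% |
| 15% | 1.00; 5% | 0.49; 22% | 0.23; 65% |
| 20% | 1.00; 5% | 0.37; 36% | 0.11; 87% |

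If the shifted women do worse than average (m = 5%, d = 10%), the ratio goes the other way, to 1.25, with 7% rejection. So two conditions are needed: allocation shifts treatment received, and the women who shift differ in outcome. If either fails, there is no distortion. A spurious ratio opposite in direction to a real interaction would mask it.

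**Step 2. The delay mechanism.** Simulation of 3 million women per arm. Assumptions: fecundity varies between women (gamma, shape 2, mean 1), natural conception averages 0.017 per month, half are planned for IVF, conception averages 0.06 per month once IVF starts, and IVF starts uniformly between months 1 and 6 in controls and later by the stated delay in the intervention arm. Conception before month 6.26 counts as a live birth within 15 months. Resection has no effect on conception.

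| IVF delay (months) | By treatment received: IVF / no IVF | By plan at randomisation: IVF / no IVF |
|---|---|---|
| 0 | 1.00 / 1.00 | 1.00 / 1.00 |
| 1 | 0.64 / 1.09 | 0.81 / 1.00 |
| 2 | 0.37 / 1.16 | 0.67 / 1.00 |
| 3 | 0.18 / 1.21 | 0.56 / 1.00 |
| 3, IVF otherwise starting within month 1 | 0.45 / 1.45 | 0.62 / 1.00 |

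Grouped by plan, the odds ratio below 1 in the IVF group is the true effect of starting IVF later, and the no-IVF group correctly shows nothing. Grouped by treatment received, the first is exaggerated and the second shows a benefit that does not exist.

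**Step 3. With a real effect.** If resection doubles conception and IVF starts 3 months later, the odds ratios by treatment received are 0.34 / 2.46 and by plan 1.15 / 2.05. Resection would look harmful in IVF recipients although its net effect in women planned for IVF is slightly favourable.

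**The case against.** A reader might infer that allocation is certain to change treatment received and that the analysis will therefore report subgroup effects that do not exist. The documents do not support that. Section 11.2 says that IVF may differ and makes its adjustment conditional on this. With no delay, or with shifted women of average prognosis, the calculations show no distortion.

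Other points on that side stand in part:

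- The delay is not universal. Where women are randomised during hysteroscopy (Pathway 2, section 5.3), resection happens in the same procedure. Women may also be approached early in an ART cycle, so treatment type may be partly settled for them. Conceiving naturally does not rule out later IVF, for example after a miscarriage.
- The odds ratio of 0.18 is an extreme point. With a 3-month delay, intervention IVF starts between months 4 and 9, and (9 − 6.26)/5 = 55% of those starts fall too late for a birth by 15 months. The simulated control live birth rate is 14.4%, against the protocol's 10%. The 3-month case also contains a real difference between subgroups, 0.56 against 1.00, so it shows exaggeration and not an interaction made from nothing. Step 1 shows that the latter is possible.
- The analysis is labelled exploratory, and the authors plainly know that IVF may differ by arm.

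The last point does not rescue the analysis. The label lowers the weight given to a result but leaves its bias in place. The weighted analysis is conditional, targets an effect in the absence of IVF, and is not linked to this interaction.

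**Conclusion.** The concern holds in a limited form. Subgroup (b) is a post-randomisation variable that the protocol itself treats as an outcome and expects may differ by arm for IVF. If it does differ and the women who shift differ in prognosis, the interaction can create, exaggerate or hide effect modification, and it cannot be read as showing in whom resection works.

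The size is unknown, because the protocol gives neither IVF uptake nor delay. Under the assumptions above, the false-positive rate of the interaction test with no effect present runs from 5% to 87% at 560 women. The odds ratios by treatment received run from no distortion to 0.18 with IVF and 1.45 without, in different scenarios. These figures illustrate the mechanism and do not predict the result.

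Subgroup (a) is a randomisation stratum and is sound. The primary intention-to-treat comparison and the sample size are not affected.

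**What to change.** Redefine subgroup (b) in section 11.2 as the fertility treatment planned at randomisation, in the classes expectant, ovulation induction, IUI and IVF/ICSI, recorded before allocation. Add the item to the baseline column of Table 2. Report treatment received by arm descriptively, as the secondary outcome it already is, and do not use it as a subgroup.

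The cost is one baseline item and a wording change; no trial procedure or sample size changes. For women already enrolled, take the plan from notes dated before randomisation where they show it, and class the rest as not recorded. Nothing in the protocol shows how often those notes state a plan, so recovery may be incomplete.

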Intervention arm only

IP = in person, MN = medical notes

T = telephone contact with patient

Q = questionnaire, administered via post/email/online

NHSD = NHS Digital

Long term follow-up

Long term follow-up data will be collected 5 years after the final patient was recruited in one of two ways;

- 1) The clinic / hospital in which participants were randomised will be asked to check the medical records of those who gave consent for long term data collection. If the patient commenced treatment elsewhere, telephone or postal contact may be made with the participant by a member of the clinical research team.
- 2) An application will be made to NHS Digital requesting access to data from those who have agreed to this on the consent form. The names, date of birth and NHS number will be sent to NHS Digital for data linkage. Accessing data from NHS Digital is likely to result in increased data completeness compared to following up participants manually over this time frame, due to the likelihood of participants changing address and the risk of a low response rate (if followed up via questionnaire) or being discharged from the recruiting centre and receiving treatment/maternity care at another hospital (if followed up using local medical records).

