11.1 Sample size

The primary outcome for both trials will be live birth rate (LBR) defined by the number of live births after 24 weeks gestation within the 15-month post-randomisation follow-up period relative to the number of women randomised.

Our review of the research literature including a Cochrane review of hysteroscopic removal of submucous fibroids and endometrial polyps (6) has found no reported estimates of the LBR in our proposed target populations. Although, two previously conducted RCTs included in the Cochrane review roughly indicate a doubling of pregnancy rates. The first quoted a clinical pregnancy rate (at 6-7 weeks) of approximately 214/1000 (21%) over 12 months in a sample of 42 women with fibroids (submucosal and mixed submucosal intramural) without surgery and a miscarriage rate (between 7 and 12 weeks) in those without surgery of approximately 556/1000 (56%) (35). Applying the miscarriage rate to the pregnancy rate (i.e. $0.21 * 0.56$) would give a LBR of approximately 10% over 12 months in the control arm (no resection). The second, in women with endometrial polyps undergoing IVF, detected an increase of pregnancy rates from 28% to 63%, with no miscarriage rate reported (36). We therefore estimate a usual care LBR of 10% within 15 months in the populations of women proposed for inclusion in this study, both for the submucous fibroid and endometrial polyp RCTs.

Assuming a 10% LBR in the no hysteroscopic removal (control) group and that an absolute increase of 10%, to a 20% LBR (a relative risk of 2.00) in the hysteroscopic removal (intervention) group is of clinical and practical importance. Then to have a 90% power of detecting this difference or more, in LBR rates between the groups, as statistically significant at the 5% two-sided level, will require 266 women per group (532 in total). Adjusting for a predicted attrition rate of 5% (due to potential difficulties of follow-up for patients who have been referred from other NHS Trusts) we will require 560 participants to be randomised.

A similar sample size will be required for RCT2 (polyp population) i.e. 560 participants, so a total of 1120 participants are required for RCT1 and RCT2 combined.

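### After 24 months Table 2 drops telephone contact for births and pregnancies, contrary to section 9.1, while the time-to-event analyses run on to last patient last visit

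*Protocol*

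**What the plan says.** **Analysis.** Protocol section 11.2 (time to event outcomes) follows every woman for at least 2 years and the first recruits for up to 4.5 years. The censoring rule is: "Women will be censored at the last known date of follow-up if they have not had a live birth/clinical pregnancy".

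**Table 2.** Time to live birth, time to pregnancy, miscarriage and still birth are marked T/MN (telephone or medical notes) at 15 and 24 months. In the column headed "Post 24 months to Last Patient Last Visit (LPLV" the same rows show MN only. The vaccination-status row in that column shows T/Q (telephone or questionnaire).

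**Section 9.1 text.** The paragraph for 24 months is headed as extending to LPLV. It reads: "Members of site staff will be asked to record the following from patients' medical notes and / or telephone contact with the participant". Its list includes time to live birth and time to pregnancy.

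**Elsewhere.** For the primary outcome, section 8.2 requires a telephone call when the woman has been discharged or has started treatment elsewhere. The long-term follow-up part of section 9.1 explains why local records lose data, naming the risk of women "being discharged from the recruiting centre and receiving treatment/maternity care at another hospital (if followed up using local medical records".

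**The concern.** Months 24 to 54 are used only by the time-to-event analyses, and they are the months for which Table 2 withdraws telephone contact about births. Whether a late birth is seen then depends on whether the woman is still under a centre whose notes are read.

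The censoring rule does not say whether an empty record counts as follow-up. If it does, a birth at another hospital becomes event-free time. If it does not, women who leave are censored early while births among those who stay are counted. Either matters for the treatment comparison if staying under the centre differs by arm. Section 2.1 suggests that resection might let some women avoid IVF, and section 11.2 says IVF use may differ between arms, so this is plausible.

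The rank-preserving and inverse-probability methods in section 11.2 address treatment switching and withdrawal, and they use the same end-of-trial data. They cannot restore births that were never recorded.

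**Working it through.** **1. The two sources side by side**

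| Period | Table 2: time to live birth, time to pregnancy | Section 9.1 text |
|---|---|---|
| 15 months | T/MN | notes, telephone or both |
| 24 months | T/MN | notes, telephone or both |
| 24 months to LPLV | MN | notes, telephone or both (same paragraph as 24 months) |

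Nothing else secures contact after month 24. The data windows in section 9 stop at 24 months, section 9.4 treats 24 months as final data collection, and section 10.2 asks women about adverse events only up to 24 months.

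**2. The protocol's own figure**

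Inputs from section 11.1: "Assuming a 10% LBR in the no hysteroscopic removal (control) group"; "to a 20% LBR (a relative risk of 2.00) in the hysteroscopic removal (intervention) group"; "90% power of detecting this difference or more"; "statistically significant at the 5% two-sided level, will require 266 women per group (532 in total".

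n per group = [z₀.₉₇₅√(2p̄(1−p̄)) + z₀.₉₀√(p₁(1−p₁)+p₂(1−p₂))]² / (p₂−p₁)²

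With p̄ = 0.15: [1.960×0.505 + 1.2816×0.5]² / 0.01 = 265.9, so 266 per group. Then 532/0.95 = 560. The stated size reproduces, so the 10% and 20% rates are a sound anchor for the next step.

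**3. Share of live-birth events after month 24**

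The protocol gives no such figure. Assumptions:
- even recruitment over 30 months, so the end of follow-up C is uniform from 24 to 54 months (section 11.2; section 4 says at least 4.5 years, but only up to 4.5 fits 24 + 30 months)
- a lag of L months before a birth is possible
- the curve fixed to 10% and 20% at 15 months.

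For a constant hazard:
- λ = −ln(1−p)/(15−L)
- F(t) = 1 − exp{−λ(t−L)}
- mean F(C) = 1 − [e^{−λ(24−L)} − e^{−λ(54−L)}]/(30λ)
- share = [mean F(C) − F(24)] / mean F(C)

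With L = 0:
- Control: λ = 0.1054/15 = 0.00702; F(24) = 0.155; mean F(C) = 0.238; share 35%.
- Intervention: λ = 0.2231/15 = 0.01488; F(24) = 0.300; mean F(C) = 0.436; share 31%.
- Pooled: (0.083 + 0.136)/(0.238 + 0.436) = 32%, or about 61 of 189 events in a trial of 560.

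Other assumptions, arms pooled:

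| Assumption | Share after month 24 |
|---|---|
| Constant hazard, lag 0 / 3 / 6 / 9 months | 32.4% / 34.5% / 36.5% / 37.7% |
| Weibull shape 0.75, lag 0 to 9 | 26% to 32% |
| Weibull shape 0.5, lag 0 to 9 | 19% to 24% |
| 30% to 70% of women never have a birth, lag 0 or 9 | 14.2% to 32.5% |
| Constant hazard, recruitment 36 months, lag 0 or 9 | 36.0% to 40.9% |
| Constant hazard, recruitment 48 months, lag 0 or 9 | 41.8% to 45.7% |

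At the planned 30 months the share is about one third under a constant hazard and roughly 15% to 38% overall.

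**The case against.** **Telephone contact is allowed.** Section 9.1 permits it up to LPLV. A reader might infer from Table 2 that late births come from the randomising centre's notes alone. The documents do not support that: it is true of one table column only, and the MN legend does not name whose notes. What remains is a contradiction that lets a site use notes alone.

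**The either/or wording also governs 15 and 24 months.** This stands in part. Section 8.2's call rule protects the primary outcome, and Table 2 still lists telephone at 24 months. It does mean that editing the cells is not enough without a rule on when to call.

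**The remark on local records concerns the 5-year follow-up**, and the same sentence warns of low questionnaire response. Both are fair. Still, discharge and delivery elsewhere lose births in month 30 as they do in year 5.

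**The analysis plan can define the censoring date.** True, but no analysis plan can recover births that were not collected.

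**NHS Digital may fill the gap.** Table 2 has a long-term entry for live birth rate and time to pregnancy but none for time to live birth. Section 7.2 also unblinds after the 24-month data, before the long-term data.

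**Stronger readings.** A reader might put the share at 40% or more. Pooled over arms, that needs a constant hazard and recruitment longer than planned; at 30 months only the control arm with a 6 to 9 month lag reaches it (40% to 42%). A reader might also attach a biased hazard ratio. If 90% of late births were found in controls and 70% to 80% in the intervention arm, the crude event ratio with no true effect and a one-third late share would be (0.667 + 0.333×0.7)/(0.667 + 0.333×0.9) = 0.93 to (0.667 + 0.333×0.8)/(0.667 + 0.333×0.9) = 0.97. Those detection rates are invented; the protocol gives none. Nor does section 11.2 say that IVF use will differ, only that it may.

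**Conclusion.** The point holds as an inconsistency with consequences for secondary outcomes. Table 2 and section 9.1 disagree on how births and pregnancies are found after 24 months, and notes-only collection satisfies both. About one third of live-birth events fall in that window under a constant hazard with the protocol's rates. The range of roughly 15% to 38% depends on the hazard shape, the lag and the share of women who never give birth, none of which the protocol states.

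Bias in the hazard ratio requires that remaining under the centre, or being found, differs by arm. That is plausible but not established, and its direction and size cannot be derived from the document. The 15-month primary outcome and the 24-month live birth rate are not touched. The change is worth making because the loss cannot be repaired at analysis and prevention is cheap.

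**What to change.** 1. Reconcile Table 2 with section 9.1: change the post-24-month cells for time to live birth, time to pregnancy and the other pregnancy outcomes from MN to T/Q/MN.
2. Ask for dates of any pregnancy and birth at the T/Q contact that the same column already lists for vaccination status, and state when that contact takes place, since section 9.1 gives no date after 24 months.
3. Extend section 8.2's rule to LPLV: telephone when the woman has been discharged or is treated elsewhere. Without this the either/or wording still permits notes alone.
4. Define the last known date of follow-up as the last direct contact or positive record. A notes review that finds nothing should not extend event-free time.
5. Optionally add a time-to-event analysis truncated at 24 months as a sensitivity analysis. It should not replace the analysis to LPLV, because it discards events and follow-up that section 11.2 means to use.

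The cost is a wording change in Table 2 and section 9.1, one or two questions at a contact already listed, and calls to women who have left the centre. Step 4 still leaves censoring related to leaving care for women who cannot be reached; steps 1 to 3 are there to keep that group small.
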